## 2. STUDY ENDPOINTS

### 2.1 Primary Efficacy Endpoints

- Change from baseline in average daily time (minutes) to first prodromal symptom associated with sunlight exposure between 1 hour post sunrise and 1 hour pre-sunset at Week 16 (Visit 8).

To calculate the average daily sunlight exposure time to first prodromal symptom, a 14-day window on or before a visit (Week 2, 4, 6, 8, 10, 12, 14, and 16) will be used. For baseline, a 14-day window before Day one will be used. A 14-day window will be applied to similar situations for other efficacy endpoints.

The subjects' diary data will be used to derive this and other endpoints based on sunlight exposure time. The details will be given in section 5.4.1. Minute will be used as unit for duration for this and other endpoints.

### 2.2 Secondary Efficacy Endpoints

- Change from baseline in average daily duration (minutes) of sunlight exposure between 1 hour post sunrise and 1 hour pre-sunset without prodromal symptoms at Week 16.
- Change from baseline in average daily mean duration (minutes) of sunlight exposure between 1 hour post sunrise and 1 hour pre-sunset without prodromal symptoms. The daily mean duration is considered as multiple periods of sunlight exposure in each day and measurable by sum of duration of each period divided by number of periods.
- Total number of sunlight exposure episodes with prodromal symptoms during 16-week double-blind treatment period.
- The average daily mean intensity of the subject's prodromal symptoms during 16-week double-blind treatment period.
- Change from baseline in average daily duration (minutes) of prodromal symptoms during 16-week double-blind treatment period.
- The change from baseline and % change from baseline in melanin density at Week 8, 16, and 22 by skin segments. Average of 6 skin segments for the change from Baseline and % change from baseline in melanin density at Week 8, 16, and 22.
- Total number of pain events during 16-week double-blind treatment period.

### 2.3 Other Efficacy Endpoints

- Change from baseline for in-clinic sunlight exposure time (minutes) to the first prodromal symptoms.
- Total time (hours) during 16-week double-blind treatment period in duration of sunlight exposure between 1 hour post sunrise and 1 hour pre-sunset without prodromal symptoms.

- Total number of days subject is exposed to sunlight for any duration between 1 hour post sunrise and 1 hour pre-sunset without prodromal symptoms during 16-week double-blind treatment period.
- Change from baseline in average daily duration (minutes) of sunlight exposure between 1 hour post sunrise and 1 hour pre-sunset on Saturday without prodromal symptoms at Week 16.
- Change from baseline in average daily duration of sunlight exposure regardless of time of day without prodromal symptoms assessed at Week 16.
- The average daily mean intensity of the subject's pain events during 16-week double-blind treatment period.
- Change from baseline in average daily duration (minutes) of pain events during 16-week double-blind treatment period.
- Change from baseline for all total score and total score in each domain of physical function, anxiety, depression, fatigue, sleep disturbance, ability to participate in social roles and activities, pain interference, pain intensity in PROMIS 57.
- Patient Global Impression of Change (PGIC).

## 2.4 Safety Endpoints

### 2.4.1 Adverse events (AEs)

An AE is any untoward medical occurrence in a subject or clinical investigation subject administered a pharmaceutical product that does not necessarily have a causal relationship with this treatment.

AEs will be coded using Medical Dictionary for Regulatory Activities (MedDRA) central coding dictionary, Version 22.0 .

Treatment-emergent AEs (TEAEs) are defined as AEs that newly occurred or worsened in severity on or after the first dose of study double-blinded (DB) treatment. The treatment relationship with the AE is in 2 categories (reasonable possibility, no reasonable possibility). The detail is included in protocol.

### 2.4.2 Physical examination

The complete physical examination consists of a routine assessment of major body systems:

- Abdominal
- cardiovascular
- general appearance
- head
- eyes
- ears/nose/throat
- lymph nodes
- musculoskeletal

- neck
- neurological
- dermatological
- other

The abbreviated physical examination consists of a routine assessment of the following body systems:

- Abdominal
- cardiovascular
- general appearance
- other

#### **2.4.3 Vital signs**

- The vital signs include:
- Sitting Systolic Blood Pressure (mmHg)
- Sitting Diastolic Blood Pressure (mmHg)
- Sitting Pulse Rate (bpm)
- Oral Body Temperature ( $^{\circ}$ C)
- Body Weight (kg)

#### **2.4.4 Clinical laboratory examinations**

The lab tests are conducted for the following lab categories

- Hematology
- Coagulation
- Biochemistry
- Urinalysis

The liver function markers (ALT, AST, GGT, ALP, direct and total bilirubin) will be collected.

The lab test names are listed in the table below.

**Table 2 Routine Laboratory Evaluations**

Hematology:	
Hemoglobin	Mean corpuscular hemoglobin
Hematocrit	Mean corpuscular hemoglobin concentration
Platelet count	Mean corpuscular volume
Red blood cell count	White blood cell count and differential
Biochemistry:	
Aldosterone	Cholesterol
Alkaline phosphatase	Triglycerides
Aspartate aminotransferase	High density lipoprotein-cholesterol
Alanine aminotransferase	Low density lipoprotein-cholesterol
Gamma-glutamyl transpeptidase	Protein (total)
Potassium	Albumin
Sodium	Creatine kinase
Chloride	Creatinine
Inorganic phosphate	Ferritin
Glucose	
Bilirubin (direct and total)	
Blood urea nitrogen	
Coagulation:	
Prothrombin time	Activated partial thromboplastin time
International normalized ratio	
Urinalysis:	
Specific gravity, pH, protein, glucose, ketones, urobilinogen, blood	
Microscopic examination a	

a Performed only if required, based on urinalysis results

### 2.4.5 ECG parameters

The 12-lead ECG will be performed and the following parameters will be collected.

- Heart rate(bpm)
- PR(msec)
- RR(msec)
- QRS(msec)
- QT(msec)
- QTcF (msec)
- QTcB(msec)

The ECG interpretation (abnormal / normal and clinically significant / not clinically significant) will be collected.

#### **2.4.6 Nevi appearance**

- Nevi appearance is assessed by a dermatologist. Any nevi that enlarge or otherwise undergo changes that are of clinical concern during active treatment will be biopsied for follow up.
- Any suspicious nevi found during assessment (Y,N)
- Any clinically significant findings (Y,N)

#### **2.5 Pharmacokinetics (PK) Evaluations**

Plasma concentrations of MT-7117 will be sampled then analyzed at randomization visit, Week 4, 8, 12, and 16 visits.

#### **2.6 Demographic and Other**

##### **2.6.1 Demographic and Baseline Characteristic**

The following subject demographic and baseline characteristic are collected.

- Age (years)
- Sex
- Race
- Ethnicity
- Weight (kg)
- Height (cm)
- BMI (kg/m^2)
- Baseline average sunlight exposure duration without prodromal symptoms
- Baseline average daily duration of pain
- Seasonality (Randomized between Mar 1 and Aug 31 inclusive, other)

##### **2.6.2 Medical History**

The subjects Medical, medication, smoking, alcohol, psychiatric disease and surgical history will be recorded. Medical/surgical history includes any medical condition or surgical history before Screening. In addition, the detailed history of hepatic disease or injury (e.g., viral hepatitis, autoimmune hepatitis, nonalcoholic steatohepatitis, hypoxic/ischemic hepatopathy, or biliary tract disease) will be recorded.

##### **2.6.3 Prior or Concomitant Medications**

Prior medications are defined as any medication taken before Screening.

Any prior medication, including prescription and over-the-counter medications, taken within 1 month before Screening will be recorded on the eCRF. Information recorded will include: name of medication, dose, duration of and reason for use.

Concomitant medication is defined as any medication, other than study medication, which is taken during the study after Screening, including prescription, over-the-counter medications, herbals, dietary supplements, and recreational drugs. All concomitant medications taken while the subject is participating in the study will be recorded.

The prior and concomitant medication data will be coded using World Health Organization Drug Dictionary (WHO-DD).

## **2.7 Fitzpatrick Skin Type Assessment**

The Fitzpatrick scale test will be completed at screening, Week 8, and 16.

The Fitzpatrick scale (also Fitzpatrick skin typing test; or Fitzpatrick phototyping scale) is a numerical classification schema for human skin color, developed in 1975 by Thomas B. Fitzpatrick as a way to estimate the response of different types of skin to ultraviolet light.

Fitzpatrick scale test is presented in protocol Appendix 2.

## **2.8 Subject Questionnaire for Study Medication**

Subject will be asked whether they receive active or placebo treatment at Week 16 or early termination. The results will be recorded on the eCRF.

## **2.9 Protocol Deviations**

Protocol deviations will be documented, reviewed and determined in the blinded data review meeting (BDRM). Protocol deviations potentially influencing the evaluation of the primary endpoint will be defined as major deviations in order to define PP population in Section 4.3. The major protocol deviations will be selected in this meeting.

At least the following will be included as major protocol deviations:

- I/E criteria violation with significant impact on efficacy
- Overall drug compliance is less than 80% or greater than 120%
- Taking wrong treatment

The BDRM meeting minutes will serve as the main document for protocol deviations.

## **2.10 Exploratory Endpoints**

- Biomarker assessments using pharmacodynamics skin biopsy samples for those subjects who have given their consent
- PGx analysis including MC1R, with SNPs for those subjects who have given their consent
- Porphyrin and protoporphyrin levels

## **2.11 Exit interview and PGIC\_2**

Questionnaires for exit interview and PGIC\_2 at follow up visit are added in protocol amendment 2. Due to the late stage of the study, limited subjects have chance to finish these questionnaires. These data will not be included in the clinical data base.

## **3. PLANNED ANALYSES**

### **3.1 Interim Analyses**

An interim analysis is not planned for this study.

### **3.2 Final Analysis**

The final analysis will be conducted with unblinded data after database lock.

All the planned efficacy and safety analyses in this SAP will be performed by [REDACTED] (CRO).

## **4. ANALYSIS POPULATION(S)**

### **4.1 Safety (SAF) Population**

Safety (SAF) Population includes all randomized subjects who received at least 1 dose of study medication. The safety population will be used for all safety analyses. The subject Actual treatment received will be used for safety analyses. For subjects took more than one treatment, the highest dose level will be used for safety analyses.

### **4.2 Intent-to-treat (ITT) population**

Intent-to-treat (ITT) population: includes all randomized subjects who have at least 1 dose of study medication and who have at least 1 post-baseline efficacy assessment. The ITT population will be used for all efficacy analyses. The subject randomized treatment will be used for efficacy analyses.

### 4.3 Per-protocol (PP) population

Per-protocol (PP) population: includes all ITT subjects who do not have any major protocol deviations which have significant impact on primary analysis and complete Week 16 (the end of double-blind treatment period). The PP population will be used for primary analyses. The subject randomized treatment will be used for efficacy analyses.

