4.5 Withdrawal of Individual Subjects

A subject will be withdrawn from study if ANY of the following criteria are met:

1. The subject requests to voluntarily withdraw from further participation in study.
2. The subject is significantly noncompliant with the protocol.
3. Continuing in the study would be detrimental to the subject's safety in the opinion of the Investigator, e.g.,
 - a. The subject experiences intolerable AEs or SAEs.
 - b. The subject has clinically significant changes in safety parameters at any of the post-dose time points, as confirmed with a repeat assessment performed as soon as possible after the initial out-of-range result.
 - c. If there are any clinically significant adverse findings from post-baseline nevi evaluation, subjects will not be allowed to continue taking study medication (see Section 6.9.4). If biopsy findings are benign, subject may reinitiate study treatment based on investigators discretion.
 - d. Development of any clinically significant liver dysfunction, as follows:
 - i. ALT or AST $>6 \times$ ULN.
 - ii. ALT or AST $>4 \times$ ULN for more than 2 weeks.
 - a) Elevated total bilirubin $>2 \times$ ULN and ALT or AST $>2 \times$ ULN or
 - b) Symptoms consistent with liver dysfunction (e.g., fatigue, nausea, vomiting, abdominal pain or tenderness, fever, rash, eosinophilia $>5\%$) with concomitant ALT or AST values $>3 \times$ ULN.

Subjects (meeting above criteria) do not require withdrawal if alternative etiology is identified on discussion with the Study Medical Monitor.

Subjects meeting above criteria (with or without alternative etiology) should be reported as hepatic AE of special interest (AESI) (see Section 8.3).

These subjects will be discontinued from treatment but may be managed on study per the Investigator's discretion and followed per protocol (see Section 8.6). In addition, a subject may be withdrawn from treatment at any time for reason(s) other than those listed here.

If a subject is discontinued prematurely from the treatment or the study, the date the subject is withdrawn and the reason for withdrawal will be recorded on the site source documents and in the electronic Case Report Form (eCRF). Subjects who withdraw or are withdrawn from study treatment should be encouraged to complete all study visits and study procedures as outlined in the protocol.

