In case of permanent discontinuation from study, the end of treatment and follow-up visit assessments should be performed, as completely as possible (Sections 5.3.2.7 and 5.3.3, respectively). Unresolved AEs and SAEs will be followed up on according to Section 8.10.

For discontinued subjects who will not revisit the clinic, the site will perform scheduled phone calls for the collection and source documentation for safety information (AEs, concomitant medication, and date of last dose of medication). Return of unused medication and any other materials (e.g., diary) will be performed by courier where allowed.

In the event that a subject elects not to return to the study site for the end of treatment or Follow-up visit, the Investigator must make every effort to contact the subject to review/capture all AEs, assess dosing compliance, review concomitant medication and make every effort to complete all end of study assessments.

Subjects withdrawn from the study following randomization onto double-blind treatment may not re-enter the study. Subjects withdrawn from treatment may remain on study and continue with study procedures off treatment based on the Investigators clinical discretion.

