10.1.1 Analysis Populations

- Safety population: includes all randomized subjects who received at least 1 dose of study medication.
- Intent-to-treat (ITT) population: includes all randomized subjects who received at least 1 dose of study medication and who have at least 1 post-baseline efficacy assessment.
- Per-protocol (PP) population: includes all ITT subjects who do not have any major protocol violations and complete Week 16 (the end of double-blinded treatment period).
- PK population: includes all randomized subjects who receive at least 1 dose of study medication and who have at least 1 post-dose value of plasma concentration time point to be included in the PK analysis without important protocol deviations which may affect the PK of study medication.

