#### 5.4.1.1 The average daily time to first prodromal symptom associated with exposure to sunlight

The following is the procedure to calculate the average daily time to first prodromal symptom associated with exposure to sunlight.

1. If the sunlight exposure time is beyond the interval (from 1 hour post sunrise to 1 hour pre-sunset), then this time is excluded by comparing the sunrise/sunset time.
2. The time to first prodromal symptom associated with exposure to sunlight in a day is calculated. It is the sum of the sunlight exposure time before the first prodromal symptom occurred in the day. If a subject had sunlight exposure but no prodromal

symptom in a day, the sum of the sunlight exposure time for the day is used as the sunlight exposure time to the first prodromal symptom.

3. A diary day is qualified if the subject had non-zero duration of sunlight exposure in the day.
4. The average daily sunlight exposure time to the first prodromal symptom at a time point (Baseline, Week 2, 4, 6, 8, 10, 12, 14, 16, and 22) is the average of the sunlight exposure time to the first prodromal symptom of qualified days in the corresponding 14-day window. At least 1 day diary data is required for each 14 day window to be qualified for this calculation.
5. The minute is used as the unit for calculation of the duration. The Duration will not be rounded. However, in data presentation for listings, the duration will be rounded to integer. HH:MM can be used when the duration is more than 60 minutes. For tables, the duration will be rounded to integer for minimum and maximum and to one decimal place for mean, SD, median and confidence intervals.

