#### 7.2 Disposition of Subjects

The number of subjects who completed or prematurely discontinued from the study, the reasons for discontinuation, and the number of subjects in each analysis population will be summarized by treatment group.

The number of subjects who enter screening will be summarized, and the percentage of these subjects who fail to meet entry criteria will be reported for total subjects. Screen failures will be summarized in total and by each reason for screen failure.

The data listing for Subject disposition will be generated.

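### The per-protocol rules can keep a subject who took no study drug during the Week 16 diary window, because completing Week 16 is not defined by treatment and compliance is judged only overall

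*SAP*

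**What the plan says.** **PP set.** Protocol 10.1.1 requires no "major protocol violations and complete Week 16 (the end of double-blinded treatment period"). SAP 4.3 uses the same completion criterion, admitting ITT subjects with no major deviations of "significant impact on primary analysis and complete Week 16 (the end of double-blind treatment period"). Neither mentions drug intake at Week 16.

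**Staying on study off drug.** Protocol 4.5 states: "Subjects withdrawn from treatment may remain on study and continue with study procedures off treatment based on the Investigators clinical discretion". It adds that subjects who leave treatment "should be encouraged to complete all study visits and study procedures as outlined in the protocol".

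**Week 16 value.** SAP Table 4 fixes the window at Days 99 to 112 from first dose. SAP 5.4.1.1 sets a low data requirement and no on-drug condition: "At least 1 day diary data is required for each 14 day window to be qualified for this calculation".

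**Compliance.** SAP 2.9 opens its list with "At least the following will be included as major protocol deviations", and the compliance item reads "Overall drug compliance is less than 80% or greater than 120" (percent). SAP 5.4.10 and 5.4.11 measure compliance over the time from first treatment to the end-of-treatment visit. Table 5 defines that visit as the Week 16 visit or the visit at early termination of the study. SAP 7.9 uses the same overall range. Protocol 7.3 instead calls a subject non-compliant at 80% or less, or 120% or more, in any interval between consecutive visits.

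**Disposition.** SAP 7.2 tabulates "The number of subjects who completed or prematurely discontinued from the study, the reasons for discontinuation" and the size of each analysis population. It has no count of treatment completion. Protocol 4.5 requires the date and reason to be recorded for stopping either treatment or study.

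**The concern.** SAP 7.11.1 repeats the primary model in the PP population as the supportive analysis. A reader will take that result as the effect in subjects treated as planned up to Week 16. If some of them had stopped drug before the window opened, the PP result does not answer that question, and it moves closer to the all-data ITT result it is meant to complement.

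The imbalance could differ by arm. Protocol 4.5 ties stopping of study medication to nevus and liver findings, and Protocol 1.5 attributes the nevus changes seen in Phase I to the drug's pharmacology. The disposition table would not show how many subjects per arm had stopped drug before the primary endpoint was measured.

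**Working it through.** The plan gives no figure to reproduce, since the sample size has no formal calculation. The check applies the SAP's own compliance formula.

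**Inputs**
- Week 16 window: Days 99 to 112 (SAP Table 4).
- Exposure = end-of-treatment visit date − first distribution date + 1 (SAP 5.4.10), which equals the study day of Visit 8. Call it V.
- Compliance = (exposure − days missed) / exposure (SAP 5.4.11).
- V = 113, allowed range 106 to 120 (Protocol 5.3.2.7).
- Excluded if compliance is below 80% (SAP 2.9).
- Assumption: every dose is taken up to last-dose day L, and every later day counts as missed.

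**Step 1: which stop days pass.** Compliance is then L / V. The subject stays in PP if L ≥ 0.80 × V. No dose falls in the window if L ≤ 98.

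| Visit 8 (V) | 0.80 × V | Last-dose days that pass | Compliance, earliest | Compliance, latest |
|---|---|---|---|---|
| 106 | 84.8 | 85 to 98 (14 days) | 85/106 = 80.2% | 98/106 = 92.5% |
| 113 | 90.4 | 91 to 98 (8 days) | 91/113 = 80.5% | 98/113 = 86.7% |
| 120 | 96.0 | 96 to 98 (3 days) | 96/120 = 80.0% | 98/120 = 81.7% |

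Earlier stops fall below 80% and are excluded.

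**Step 2: how days after the stop are counted.** SAP 5.4.11 does not say whether days after a permanent stop are missed days. If they are not, or if the end-of-treatment visit is dated at the treatment stop, compliance is about 100% for any L and the rule excludes nobody. Step 1 is therefore the reading more favourable to the SAP.

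**Step 3: the protocol's interval rule.** Take the latest stop, L = 98, and the Visit 7 to Visit 8 interval.
- Nominal days (85 and 113): (98 − 85)/(113 − 85) = 13/28 = 46%, or 14/29 = 48% if the Visit 7 day is counted.
- Lowest over the allowed days (Visit 7 on Day 92, Visit 8 on Day 120): 6/28 = 21%.
- Highest (Visit 7 on Day 78, Visit 8 on Day 106, counting the Visit 7 day): 21/29 = 72%.

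Earlier stops give lower values. Every subject with a Visit 7 and a last dose by Day 98 is therefore non-compliant under Protocol 7.3, yet those in the table pass SAP 2.9.

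**The case against.** Several points on the other side are sound.

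- A reader might infer that PP is built on attending the Week 16 visit rather than on completing treatment. The text does not say so. The word visit is absent, and the parenthesis links completion to the treatment period. The criterion is ambiguous, and the on-treatment reading would close the gap.
- The list in SAP 2.9 is a minimum. SAP 2.9 defines major deviations as those that could influence evaluation of the primary endpoint, and SAP 7.1 lets the blinded review add data handling rules. The review could remove these subjects. Nothing requires it to, and a foreseeable case is better settled in the SAP.
- A reader might infer that being off drug while on study can never be a deviation because the protocol permits it. No section says that, and Protocol 7.3 classes such subjects as non-compliant.
- A reader might infer that off-drug subjects are invisible unless an adverse event made them stop. SAP 7.8 summarises total dosed days beside duration of exposure, and SAP 7.9 lists accountability by subject. What is missing is a direct count by arm of who had stopped before Day 99.
- The disposition table is tied to completing the study, which runs to Week 22, and not to the Week 16 visit.
- The analysis is supportive, in a trial the protocol calls exploratory. SAP 4.3 does say that PP will be used for primary analyses, but SAP 7.11.1 makes its supportive role clear.

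These points narrow the concern but do not remove it. As written, the stated compliance rule passes subjects whom the protocol's own rule would flag.

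**Conclusion.** The concern holds in limited form. At nominal timing, eight last-dose days (91 to 98) let a subject pass the listed PP rules with no dose in the whole Week 16 window. At the Visit 8 limits this becomes 14 days (Day 106) or 3 days (Day 120). This assumes full dosing up to the stop, later days counted as missed, the on-study reading of completing Week 16, and no added rule from the blinded review.

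The number of subjects cannot be computed, because neither document gives a discontinuation rate. For scale, one subject is 1/34 = 2.9% of an arm as randomised.

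A reader might infer a percentage shrinkage of the PP difference, or argue from plasma half-life that the effect is gone. The documents support neither. Protocol 1.5 gives Day 14 mean half-lives of 10.56 to 18.97 h. The 8 days (192 h) from Day 91 to Day 99 are 10.1 to 18.2 half-lives, while the 24 h from Day 98 to Day 99 are only 1.3 to 2.3. Clearance from plasma is also not loss of effect: the drug acts through melanogenesis, and Protocol 3.2 allows six weeks of follow-up to evaluate pigmentation recovery. Off drug here means only that no dose was taken.

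The primary ITT analysis is unaffected. This is a cheap improvement to a supportive analysis and to reporting.

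**What to change.** 1. **SAP 4.3:** define completing Week 16 as no permanent stop of study drug before the end of the Week 16 diary window (Day 112). Because Visit 8 may fall as early as Day 106, add that a subject who finished treatment as planned at a Visit 8 before Day 112 still counts as a completer.
2. **SAP 2.9:** apply the Protocol 7.3 interval rule at least to the Visit 7 to Visit 8 interval. This is preferable to a new dose-count threshold within Days 99 to 112, because missed doses may be captured only as counts between visits. Reconcile the boundary too: exactly 80% is compliant in SAP 7.9 and non-compliant in Protocol 7.3.
3. **SAP 5.4.11:** state that days after a permanent stop count as missed up to the end-of-treatment visit.
4. **SAP 7.2:** add treatment completion and discontinuation by arm, separate from study completion, with reason, day of last dose and number off drug before Day 99.

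The cost is SAP wording and some extra table rows from data the protocol already records. The downside is that a few subjects may leave the supportive PP set.
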